The proposed protocol for this study differs from other early intervention studies. The current proposal will provide a greater amount of under-correction and will occur at a younger age. Results from a longitudinal study performed by the primary investigator of this study suggest that 1.00D of under-correction in a three-month old infant would result in a very small change between 3 and 9 months of age (Figure 1) (Mutti et al., 2005). Previous studies have used only 1.00 to 2.00D of under-correction in early intervention (Atkinson et al., 2000; Ingram et al., 2000). Based on the information provided in Figure 1, the range of effective emmetropization occurs between +1.00D and +4.00D of hyperopia. More aggressive under-correction (greater than 1.00D to 2.00D) would be needed in higher hyperopes to ensure that they reach the range of effective emmetropization between +1.00D and +4.00D. The effective range of emmetropization is addressed in more detail in Figure 2. If the emmetropization endpoint is defined as reaching a refractive error of $\leq +2.00$ D by 18 months of age, then 80% or more of early refractive errors of +4.00D or less at 3 months of age will resolve by 18 months of age using no intervention. For early refractive error between +5.00D to +7.00D, which is what is proposed in this study, the percentage that reach the emmetropization endpoint of $\leq +2.00$ D drops to between 50% and as low as 20%. The range of refractive errors outside of +5.00D and +7.00D appears to be outside of the effective range of emmetropization.

Previous studies initiated early correction treatment in the latter half of the first year of life (Atkinson et al., 2000; Ingram et al., 2000). The majority of the emmetropization process occurs before 9 months of age (Mutti et al., 2005). As children get older, hyperopia becomes less effective in promoting refractive changes. Hyperopic infants between 3 and 9 months of age show a decrease of hyperopia by an average of 0.81D while infants between 9 and 18 months show a decrease of only 0.23D (Mutti et al., 2009). Perhaps previous studies did not find a treatment effect because they initiated treatment too

[figure not shown]

Figure 1. The change in hyperopia between 3 and 9 months as a function of hyperopia at 3 months.

[figure not shown]

Figure 2. The probability of emmetropization at 18 months ($\leq +2.00$ D) as a function of refractive error at 3 months.

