- vii. **Peripheral refractive error.** Peripheral refractive error will be assessed by the examiner using the SureSight autorefractor as an estimate of the ocular shape during emmetropization. The subject's gaze is directed towards toys or interesting targets. Measurements will be made at 30° in both left and right gaze (a total of 2 peripheral gazes). This will be measured at the baseline, 9 month, and 18 month visit.
- viii. **Parental refractive error status.** The parent(s) refractive error will be obtained as in the Berkeley Infant Biometry Study (BIBS), from the prescription for glasses provided by the eye care provider for parents who wear refractive correction. If the parents report not having had a recent eye

examination, refractive error status will be estimated with the autorefractor without cycloplegia.

ix. Survey. Additional data will be collected via a survey administered at the baseline visit and will request information regarding:

1. Parental age at the infant's birth
2. Parental smoking status
3. Alcohol consumption
4. Infant birthweight
5. Birth order
6. Minor complications of pregnancy and delivery
7. Years of education completed for each parent
8. Family income
9. Ethnic identification for each parent and for the child (assigned by the parent)

x. Additional data. The following data will be obtained at each visit:

1. Significant infant illness
2. Medications given to the infant
3. Nutritional history
4. Compliance with spectacle wear. Parents will fill out a form at each follow up visit listing how compliant the subject was wearing spectacles. Parents of the subjects will be able to classify compliance as very good ($\geq 75\%$ of the time), good ($\geq 50\%$ of the time but less than 75% of the time), fair ($\geq 25\%$ of the time but less than 50% of the time), or poor ($\leq 25\%$ of the time). Parents will be given a pre-printed calendar to help them keep track of compliance on a daily basis. This will be turned into the investigator at the next follow up.

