The basic analysis will be a two-sample t-test comparison of the change in refractive error between the two groups at 9 months and again at 18 months of age. Analysis of Covariance (ANCOVA) will be used to compare the change in refractive error between the two treatment groups adjusting for any possible confounding variables. Refractive error at 3 months along with any other identified confounders will be included as covariates in the analysis. Randomization of infants into the two treatment groups should protect against confounding, however, testing will be performed and adjustments made for imbalances in confounders between groups.

The relationship of accommodative effort and accommodative lag with change in refractive error between 3 and 9, or 3 and 18 months will be analyzed by repeated measures analysis of variance. We will fit a linear functions describing the relationship between change in refractive error and accommodation as the repeated factor, either effort or lag. A significant effect for type of accommodation will indicate that the greater slope is the better explanation of the driving force for change in refractive error.

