Relative peripheral refractive error will be calculated as the difference in peripheral and central cycloplegic refractive error. This relative peripheral refractive error calculation will give insight into the ocular shape of the subject. If the relative peripheral refractive error is relatively myopic compared to the central refractive error, the eye has a more oblate shape. If the relative peripheral refractive error is relatively hyperopic compared to the central refractive error, the eye has a less oblate or more prolate shape. The relationship of the change in peripheral refractive error and central refractive error (relative peripheral refractive error) will be analyzed by a two-sample t-test comparison of the change in the relative peripheral refractive error between the two groups at 9 months and again at 18 months of age. Analysis of Covariance will be used to compare the change in relative peripheral refractive error between the two treatment groups adjusting for any other possible confounding factors. Peripheral refractive error at 3 months along with any other identified confounders will be included as covariates in the analysis. Randomization of infants into the two treatment groups should protect against confounding, however, testing will be performed and adjustments made for imbalances in confounders between groups.

IV. Bibliography

Blade, P.J. & Candy, T.R. (2006). Validation of the PowerRefractor for measuring human infant refraction. *Optom Vis Sci*, 83, 346-53.

Cook, R.C. & Glasscock, R.E. (1951). Refractive and ocular findings in the newborn. *Am J Ophthalmol*, 34, 1407-13.

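### The ANCOVA of change in relative peripheral refraction names absolute peripheral refraction as its baseline covariate, so it adjusts only partly for the outcome's own baseline and usually loses some precision

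*Combined protocol and SAP*

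**What the plan says.** Section F defines the outcome: "Relative peripheral refractive error will be calculated as the difference in peripheral and central cycloplegic refractive error". Its change is compared between the randomized groups at 9 and 18 months, first by a two-sample t-test and then with adjustment: "Analysis of Covariance will be used to compare the change in relative peripheral refractive error between the two treatment groups". The named baseline covariate is in the next sentence: "Peripheral refractive error at 3 months along with any other identified confounders will be included as covariates in the analysis". The word *relative* is absent there.

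Two other places bear on the meaning. Section D.c.vii uses the term for the off-axis readings themselves, taken at 30° in left and right gaze: "Peripheral refractive error will be assessed by the examiner using the SureSight autorefractor as an estimate of the ocular shape during emmetropization". On timing it adds: "This will be measured at the baseline, 9 month, and 18 month visit". The parallel ANCOVA of central refraction, earlier in section F, adjusts for its own outcome at baseline: "Refractive error at 3 months along with any other identified confounders will be included as covariates in the analysis".

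Both ANCOVA paragraphs end with a general provision: "testing will be performed and adjustments made for imbalances in confounders between groups". It lists no variables.

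**The concern.** Read literally, the outcome is a change in one quantity and the covariate is the baseline of another. A change score is normally negatively related to its own starting value, and adjusting for that value is what recovers precision and corrects for chance differences between groups at baseline. Absolute peripheral refraction is central plus relative refraction, so it measures baseline relative refraction with the level of central refraction mixed in.

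The objective in section I predicts that treatment works by changing ocular shape, and relative peripheral refraction is the plan's measure of shape. The sample size section requires 13 evaluable infants per randomized group, so there is little precision to spare.

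**Working it through.** **Inputs.** The documents give no SD, correlation or sample size for relative peripheral refraction, so there is no figure of the plan's to reproduce. The 13 per group was sized on central refraction and serves here only as the number available (2 × 13 = 26). Everything else below is an assumption shown over a range.

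**Notation.** R0 and R1 are relative refraction at baseline and follow-up, with equal variances set to 1 and correlation ρ. C0 is central refraction at baseline. P0 = C0 + R0 is absolute peripheral refraction at baseline. The outcome is D = R1 − R0. In the base case C0 is uncorrelated with R0 and has no direct effect on D. Let k = SD(C0)/SD(R0) and λ = 1/(1 + k²), the squared correlation of P0 with R0.

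**Residual variance of D.**
- No covariate: 2(1 − ρ)
- Adjusted for R0 (own baseline): 1 − ρ²
- Adjusted for P0 (as written): (1 − ρ)[2 − (1 − ρ)λ]

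The ratio of the third to the second is [2 − (1 − ρ)λ]/(1 + ρ). At ρ = 0.5 and k = 1 (λ = 0.5) it is (2 − 0.25)/1.5 = 1.17. The standard error is then √1.17 = 1.08 times as large, and 26 infants carry the information of 26/1.167 = 22.3.

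| ρ | k = 0.25 | k = 0.5 | k = 1 | k = 2 | no covariate |
|---|---|---|---|---|---|
| 0.3 | 1.03 | 1.11 | 1.27 | 1.43 | 1.54 |
| 0.5 | 1.02 | 1.07 | 1.17 | 1.27 | 1.33 |
| 0.7 | 1.01 | 1.04 | 1.09 | 1.14 | 1.18 |
| 0.9 | 1.00 | 1.01 | 1.03 | 1.04 | 1.05 |

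The last column is the ceiling, approached when P0 says almost nothing about R0. So the ratio runs from 1.00 to 1.43 over this grid and cannot exceed 1.54 for ρ of 0.3 or more under these assumptions.

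**Where k may lie.** Section II describes the randomized range: "For early refractive error between +5.00D to +7.00D, which is what is proposed in this study". If central refraction is uniform over it, its SD is 2/√12 = 0.58D. An SD of relative refraction of 0.5D, 1.0D or 1.5D (assumed) then gives k = 1.15, 0.58 or 0.38, and at ρ = 0.5 a ratio of 1.19, 1.08 or 1.04. Eligibility needs only one eye to qualify, so fellow eyes may widen the central SD and raise k.

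**Chance imbalance.** The share of the effect of an R0 imbalance that remains after adjusting for P0 is 1 − λ: 6%, 20%, 50% and 80% for k = 0.25, 0.5, 1 and 2.

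**Can the direction reverse?** Let C0 have a direct slope g on D, with ρ = 0.5 and k = 1. Var(D) stays at 1. The residual variance is 1 − (g − 0.5)²/2 after P0, 0.75 after R0, and 0.75 − g² after R0 and C0 together.
- g = −0.4: 0.595/0.75 = 0.79 for P0, against 0.59/0.75 = 0.79 for the pair
- g = +0.4: 0.995/0.75 = 1.33 for P0, against 0.79 for the pair

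The written covariate can therefore beat R0 alone. It cannot leave more explained than R0 and C0 together, because P0 is their sum.

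**The case against.** **It may be shorthand.** The covariate sentence repeats the one for central refraction with one word put in front, and section D.c.vii itself calls peripheral refractive error an estimate of ocular shape. The authors may have meant the outcome's own baseline. That cannot be ruled out, but an analyst following the text would fit the absolute value, so the wording needs correcting either way.

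**The plan allows further adjustment.** A reader might infer that chance imbalance in baseline shape is left uncorrected. The documents do not support that: absolute peripheral refraction removes part of it, and the plan provides for adjusting imbalances found on testing. That provision is a weak safeguard, though. It names neither baseline relative refraction nor central refraction here. With 13 per group, a t-test flags a baseline difference of one standard error (√(2/13) = 0.39 SD) about 16% of the time and one of 0.8 SD about 50% of the time.

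**The loss may be trivial.** This stands as a limit on size. If relative refraction is stable over time, or varies much more between infants than the restricted central refraction does, the ratio is close to 1.

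**Imbalance and precision are not two separate harms.** This also stands. Under randomization, chance imbalance in a prognostic baseline averages zero and is largely what the larger residual variance already expresses.

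**Conclusion.** The mismatch is real on the literal text. The written covariate adjusts only partly for baseline relative refraction and so usually costs precision: a residual variance about 1.0 to 1.5 times that with the outcome's own baseline, and 1.17 at ρ = 0.5 with equal SDs. This rests on equal variances over time, ρ of 0.3 to 0.9, and central and relative baseline being uncorrelated. A strong negative effect of central baseline on the change would reverse it.

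Three stronger readings are tempting and not supported:
- **That the trial's only between-arm test of ocular shape is compromised.** The t-test in the same paragraph does not involve the covariate, and the primary outcome is central retinoscopy.
- **That the comparison is biased.** Allocation is randomized, so the issue is precision and chance imbalance.
- **That the loss is known and large.** A 30% larger variance, for example, needs a correlation of only 0.3 between P0 and R0 at ρ = 0.5. With a central SD of 0.58D and no central-relative correlation, that implies an SD of relative refraction of 0.58 × √(0.09/0.91) = 0.18D. Nothing in the documents supports so small a value.

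The change is worth making because it is nearly free, not because the harm is shown to be large.

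**What to change.** In section F, replace the named covariate with *relative peripheral refractive error at 3 months (same eye, same gaze)* and add *central refractive error at 3 months* as a second covariate. The pair contains the covariate now in the plan, so nothing is given up except one degree of freedom. Counting infants, that is 26 − 3 = 23 residual degrees of freedom with one covariate and 22 with two.

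Compute baseline relative refraction from the same central measure that enters the change score, and name that measure. This needs one reconciliation. The table in section D.d marks no SureSight cycloplegic reading at V1, only retinoscopy, whereas section D.c.vi has cycloplegic refractive error measured at all visits with SureSight also performed. The two should be brought into agreement so that the central reading to be subtracted at baseline is clear.

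Baseline relative refraction is already needed to form the change, so once the central reading is settled no additional measurement is required for the covariate.
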